## 5.9. Efficacy Evaluation

The primary objective of the final amended version of the study protocol (see Section 1.1) is to evaluate the efficacy of HMTM 16 mg/day compared with control over 52 weeks in patients with AD using the MMRM (including the nominal visits Week 13, Week 26, Week 39 and Week 52), including the randomization stratification variables (see Section 2.6) as fixed factors, the respective efficacy Baseline value as covariate, and the treatment indicator (plus its interaction term with the visit variable). The co-primary endpoints are the difference between HMTM 16 mg/day and control in ADAS-cog11 and ADCS-ADL23 at Week 52.

The next section will give the definitions of the estimands, which are then used in the following efficacy endpoint analysis sections. As a reminder to Section 5.2 the pre-defined analysis sequence is MITTv5 analysis followed by the estimands analysis based on ITTv5. Despite the definition of this sequence, the MITT based analysis is primary for the FDA while the ITT based analysis is considered primary for the EMA.

Regarding the MITT analyses, in subjects who have initiated treatment with an AChEI and/or memantine, assessments made after initiation of such treatment are not considered valid as they could confound the interpretation of the results and will be excluded. Such subjects and affected assessments will be identified prior to unblinding. Sensitivity analyses will be provided for the primary and selected secondary analyses including all data (MRI whole brain volume, and F-FDG-PET temporal lobe).

### 5.9.1. Estimands

Whenever analyzed, the estimands for the comparison of 8 mg/day versus control are defined analogously.

#### 5.9.1.1. Primary Estimand (ITTv5)

The Primary Estimand is designed to answer the question on the treatment effect of HMTM dose of 16 mg/day as monotherapy versus control (containing a small amount of MTC, spiked) in the targeted

---

Sponsor:	TauRx Therapeutics Ltd.		
Protocol:	TRx-237-039		
Document Version No.:	3.0	Document Date:	07-JUN-2023

population of subjects with probable AD and MCI-AD at Week 52, regardless of trial product discontinuation, based on the two co-primary endpoints.

This estimand is constructed in line with ICH E9 (R1) addendum. The five components defining the estimand of interest are:

**A. Treatment:** 52 weeks HMTM dose of 16 mg/day or matching control (containing a small amount of MTC) as monotherapy, regardless of adherence.

**B. Population:** Subjects with probable AD and MCI-AD as described by the inclusion and exclusion criteria, randomized under protocol version 5.0 or higher.

**C. Patient-level outcomes / variables:** The co-primary outcomes are the change from Baseline of the ADAS-cog11 and ADCS-ADL23 at Week 52.

**D. Population-level summary:** Population weighted least squares means difference.

**E. Intercurrent Events:** The following ICE have been identified which could prevent measurement of the primary outcome or change the interpretation of the measured primary outcome:

1. Subjects withdraw from study before the completion of 52 weeks treatment phase for non-treatment related reason
2. Subjects withdraw from study before the completion of 52 weeks treatment phase for treatment related reason
3. Initiation of AChEI and/or memantine
4. Study treatment discontinuation for any reason other than initiation of AChEI and/or memantine (including discontinuation by the Investigator if he/she judges that treatment is no longer appropriate, if the subject's clinical condition is worsening, or for AE, or due to study drug dose interruption longer / more frequent than specified in ICE #5 below) (TOTOs, see Section 4.4)
5. A dose interruption for more than 14 consecutive days or more than two occasions of dose interruptions up to a maximum of 14 consecutive days due to safety concerns and initiated by the PI (see Section 4.4)
6. Intercurrent illnesses, or initiation of medical food or medications not allowed by protocol (which will be identified during the BDRM)

Sponsor:	TauRx Therapeutics Ltd.		
Protocol:	TRx-237-039		
Document Version No.:	3.0	Document Date:	07-JUN-2023

- 7. Study treatment non-compliance, defined as <80% or >120% taking into consideration any dose interruptions (if this cannot be estimated, it does not result automatically in a non-compliance)
- 8. Deaths before the completion of 52 weeks treatment phase
- 9. COVID-19 infection
- 10. Death due to COVID-19

**Events 1** will be handled according to a hypothetical strategy as if patients have stayed on treatment.

In a sensitivity analysis all these subject withdrawals are assumed to be potentially treatment-related, which are then handled using the treatment policy approach from ICE #2.

**Events 2** will be handled using treatment policy approach reflecting Copy Incremental from Reference strategy (using data after occurrence of the ICE for the estimation, if available). Subjects who withdraw for treatment-related reasons are assumed to retain 100% of the treatment effect they had attained up to the point of withdrawal but do not continue to benefit from treatment afterwards, in other words, assuming that the clinical course post ICE for either treatment group follows control treatment group. This corresponds to the estimate  $I = (E0*w0 + E13*w13 + E26*w26 + E39*w39) + E52*(1-w0-w13-w26-w39)$ , where for instance  $E13$  is the treatment effect at Week 13 and  $W13$  is defined as the fraction of subjects who withdrew for a potential treatment-related reason, have a non-missing efficacy parameter at Week 13, and do not have any on-treatment assessments at any scheduled visit subsequent to Week 13. The fractions are calculated within the HMTM treatment group.  $W0$  refers to subjects who had no measurement taken after the baseline measurement and thus  $E0$  is zero. The estimate  $I$  will be reported as the intervention effect and will be calculated using a contrast on the LSM (see Section 5.9.2.1).

Two sensitivity analyses will be run using hypothetical strategies (not using data after occurrence of the ICE), one by imputing missing data for both treatment groups based on data seen in control group, and one by imputing missing data for each treatment group based on data seen in their own group (see Section 4.5.2).

In another sensitivity analysis the alternative assumption will be investigated, that the subjects withdrawing from treatment for treatment-related reasons do not retain any treatment effect after Baseline; the intervention effect  $I$  in this case is  $I=E*(1-w)$ , where  $E$  is the treatment effect at Week 52 and  $w$  is the fraction of

Sponsor:	TauRx Therapeutics Ltd.		
Protocol:	TRx-237-039		
Document Version No.:	3.0	Document Date:	07-JUN-2023

subjects within the HMTM treatment group who withdraw for a potential treatment-related reason up to Week 52.

**Events 3** will be handled according to the original randomized treatment group assuming they did not start AChEI and/or memantine and will be analyzed the same as ICE #2.

**Events 4** will be handled according to a treatment policy strategy, using data after occurrence of the ICE. A sensitivity analysis will be carried out using the strategy as described for the ICE #2.

**Events 5, 6, and 7** will be handled according to a treatment policy approach, using all data (also after occurrence of respective ICE).

**Events 8** will be handled as treatment failure. If the patient dies prior to Week 52, the missing assessments will be imputed by the population average in decline, calculated by visit, within the control arm.

**Events 9, and 10** will be handled with a hypothetical strategy assuming COVID-19 disease would not have happen, not using data after occurrence of the ICE.

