### **17.4.3 ITT (EMA) Analysis**

The EMA analyses will be based on the ITT population, regardless of endpoint.

Change from baseline in the respective efficacy/imaging parameter will be analyzed using a restricted maximum likelihood-based repeated measures linear mixed model or, in the case of only one scheduled post-baseline imaging or efficacy assessment, using a simple linear model (the models used are described above in Section 17.4.2). This analysis will be restricted to scheduled, on-treatment visits for subjects randomized under Protocol Version 5.0 and above (a sensitivity will be provided including data from subjects of all protocol versions). An on-treatment visit is a visit where a subject was on investigational product and not on any AChEI and/or memantine.

This provides the on-treatment effect, E, at the final time point. For each subject who withdrew from the study, the decision will be made as part of the blinded data review meeting as to whether the withdrawal was potentially treatment-related. For potentially treatment-related drop-outs, the fraction of subjects randomized to active treatment who withdrew at a given time point will be calculated. If a subject is determined to have withdrawn for non-treatment-related reasons, no further adjustment will be made as the mixed effects model correctly accounts for subjects who are missing at random.

In this intervention effect analysis, subjects who withdraw for potential treatment-related reasons are assumed to retain 100% of the treatment effect they had attained up to the point of withdrawal but do not continue to benefit from treatment afterwards. This corresponds to the estimate  $I = (E0*w0 + E13*w13 + E26*w26 + E39*w39) + E52*(1-w0-w13-w26-w39)$ , where E13 is the treatment effect at week 13. W13 is defined as the fraction of subjects who withdrew for potentially treatment-related reasons, have a non-missing imaging/efficacy parameter at Week 13, and do not have any on-treatment assessments at any scheduled visit subsequent to Week 13. The other wxx are defined likewise. Wxx is calculated for the active treatment group only. W0 refers to subjects who had no measurement taken after the baseline measurement and thus E0 is zero. This analysis will be implemented as a contrast statement and the estimate I will be reported as the intervention effect.

Annualized rate of atrophy or decline will also be analyzed in a similar fashion.

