- In another sensitivity analysis, the alternative assumption will be investigated, that the subjects withdrawing from treatment for treatment-related reasons do not retain any treatment effect after Baseline; the intervention effect  $I$  in this case is  $I=E*(1-w)$ , where  $E$  is the treatment effect at Week 52 and  $w$  is the fraction of subjects within the active treatment group who withdraw for a potential treatment-related reason up to Week 52.
- **Events 3** will be handled according to the original randomized treatment group assuming they stopped treatment and did not start AChEI and/or memantine (analyzed same as ICE #2), not using data after occurrence of the ICE.
- **Events 4** will be handled according to a treatment policy strategy, using data after occurrence of the ICE. In addition, for EMA, the analysis will be carried out using the strategy as described for ICE #2 (not using data after occurrence of the ICE).
- **Events 5, 6, and 7** will be handled according to a treatment policy approach, using all data (also after occurrence of respective ICE).
- **Events 8** will be handled as treatment failure. If the subject dies prior to Week 52, the population average in decline within the placebo arm will be imputed.
- **Events 9 and 10** will be handled with a hypothetical strategy assuming COVID-19 disease would not have happened, not using data after occurrence of the ICE.

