##### ***17.4.11.3 Analysis of Subjects Who Started AChEI and/or Memantine***

For the FDA analyses, in subjects who initiated treatment with AChEI and/or memantine at any time during the study, data after initiation of such treatment are excluded from the primary analyses as they could confound the results. Such subjects will be identified prior to

unblinding. For EMA analyses, such subjects are treated as subjects who terminated the study at the time of starting AChEI and/or memantine; a conservative post-withdrawal course is assumed for these subjects.

Data for these excluded subjects will be tabulated separately with their observed means, standard deviations, standard errors, and minimum and maximum values of selected changes in imaging and efficacy assessments. Primary reasons for initiating antidementia therapy will be provided. Furthermore, tables will be provided quantifying the number of assessments as well as time points that are impacted by these exclusions.

Sensitivity analyses will be performed including all data for these subjects. Time to event (*i.e.*, time to withdrawal in order to start AChEI and/or memantine) may also be performed if more than 10% meet this criterion; if not, the information will be tabulated.

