### 5.9.2.2. Estimand Analysis

The primary and secondary estimands (see Section 5.9.1.1, and 5.9.1.3) will be analyzed with the ITTv5 population (see Section 3.1.1) using the MMRM as described in the previous section for the MITT population.

With the estimand described in Section 5.9.1.2 the analysis of the primary estimand will be repeated for the ITT population, but without its sensitivity analyses.

Sample SAS code (will be fully validated at the analysis stage):

```

PROC MIXED DATA=dataset METHOD=REML COVTEST;
  CLASS subject treatment(REF='Control') visit severity(REF='moderate') region(REF='Europe')
  prioruse(REF='None');
  MODEL scorediff = treatment/visit severity region prioruse scorebl / SOLUTION CL DDFM=
  KENWARDROGER;
  REPEATED visit / SUB=subject TYPE=UN;
  LSMEANS treatment*visit visit / CL;
  *BY_IMPUTATION_;
  LSMESTIMATE treatment*visit "intervention effect" nw13 nw26 nw39 nw52 -nw13 -nw26 -
  nw39 -nw52 / DIVISOR=Nhmtm CL;
  LSMESTIMATE treatment*visit "intervention effect (sensitivity)" 0 0 0 nw52 0 0 0 -nw52 /
  DIVISOR=Nhmtm CL;
  RUN;

```

*nw0, nw13, nw26, and nw39* are the number of subjects within the respective HMTM treatment group who withdrew for potentially treatment-related reasons (ICE #2 in Section 5.9.1.1), have a non-missing efficacy parameter at Baseline, Week 13 (26, 39), and do not have any on-treatment assessments at any scheduled visit subsequent to Baseline, Week 13 (26, 39). With *Nhmtm* the sample size in the HMTM treatment group, *nw52* is calculated as  $nw52 = Nhmtm - nw0 - nw13 - nw26 - nw39$ . The numbers will need to be calculated before applying the analyses model (for example saved in macro variables). With respect to sensitivity analyses, *nwx* and *nw* will need to be re-calculated, when handling further ICEs as ICE #2.

The secondary estimand is analyzed using an ANCOVA, including the randomization stratification variables (see Section 2.6) as fixed factors, the respective efficacy Baseline value and the total duration of exposure (see Section 5.12.1) as covariates, and the treatment indicator; with the Kenward and Roger method used for calculating the denominator degrees of freedom for the tests of fixed effects.

Sponsor:	TauRx Therapeutics Ltd.		
Protocol:	TRx-237-039		
Document Version No.:	3.0	Document Date:	07-JUN-2023

Sample SAS code (will be fully validated at the analysis stage):

```

PROC MIXED DATA=dataset METHOD=REML COVTEST;

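### SAP Events 3 (starting an AChEI or memantine) omits the protocol's bar on later data and conflicts with the weight count, so the EMA-primary estimate is not uniquely defined

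*SAP*

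**What the plan says.** **Protocol.** Section 17.4.4 handles the start of an AChEI or memantine (Events 3) on the assumption that the drug was not started: "analyzed same as ICE #2), not using data after occurrence of the ICE". Two other sections agree. Section 17.4.3 limits the EMA model to scheduled visits on study drug and off AChEI/memantine. Section 17.4.11.3 says of the EMA analyses that "such subjects are treated as subjects who terminated the study at the time of starting AChEI and/or memantine".

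**SAP.** Section 5.9.1.1 keeps the assumption and the pointer, "assuming they did not start AChEI and/or memantine and will be analyzed the same as ICE #2", and stops there. The ICE #2 rule it points to is applied "using data after occurrence of the ICE for the estimation, if available". The SAP does call such data invalid ("assessments made after initiation of such treatment are not considered valid as they could confound the interpretation of the results and will be excluded"), but that sentence in 5.9 is limited to the MITT analyses. Section 5 defines an on-treatment visit as one off AChEI/memantine, short-term use excepted, but 5.9.2.2 does not apply the definition as a data filter for ITTv5.

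**Weights.** The ICE #2 estimate is a weighted sum of visit effects. In 5.9.2.2 the counts cover HMTM subjects "who withdrew for potentially treatment-related reasons (ICE #2 in Section 5.9.1.1"). The same section adds, for sensitivity analyses, that the counts "will need to be re-calculated, when handling further ICEs as ICE #2".

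**The concern.** Events 3 asks what would have happened without the symptomatic drug. Scores recorded on the drug cannot answer that, and they will exist: Protocol 13.1 stops study drug in starters but encourages them to continue assessments, and SAP 4.4 classes them as off-treatment but on study. The protocol background credits AChEIs with small cognitive gains, so the data would not be neutral.

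Two things are left open in the analysis that the SAP calls primary for the EMA: whether scores after the start enter the model, and whether starters receive a retained-effect weight. Two programmers working from the same SAP could produce different primary estimates. The MRI estimand takes over the rule by reference, and the PET estimand repeats the Events 3 wording, again without the exclusion.

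**Working it through.** **1. Later data, text against text.**

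| Source | Are data after the start used? |
|---|---|
| Protocol 17.4.4, Events 3 | No |
| Protocol 17.4.3, EMA model | No (on-treatment visits only) |
| Protocol 17.4.11.3, EMA | No (treated as terminated at start) |
| SAP 5.9, MITT | No |
| SAP 5.9.1.1, Events 3 | Not stated; follows ICE #2 |
| SAP 5.9.1.1, ICE #2 | Yes, where available |

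Elsewhere in the same SAP list, data use is spelled out: Events 4 and Events 5 to 7 use later data, Events 9 and 10 do not. SAP Section 10 does not list a change to Events 3.

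**2. Weights, text against text.** SAP 5.9.1.1 sends starters to ICE #2 and so to I = ΣEx·wx + E52·(1 − Σwx). SAP 5.9.2.2 builds the counts from withdrawals alone and mentions recounting only for sensitivity analyses. The protocol's weights are also withdrawal-only ("W13 is defined as the fraction of subjects who withdrew for potentially treatment-related reasons"), but its rule in 17.4.11.3 makes a starter count as terminated. The SAP has no such sentence.

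**3. The plan's own figure.** SAP 5.3 states power of 93.2% (ADCS-ADL23: effect 3.4, SD 8.5) and 96.7% (ADAS-cog11: effect 2.6, SD 5.9). With 25% withdrawal, n = 200 × 0.75 = 150 per arm. The noncentrality is 3.4/(8.5·√(2/150)) = 3.46 and 2.6/(5.9·√(2/150)) = 3.82. A two-sided 5% t-test then gives 93.2% and 96.7%, so both figures reproduce (93.4% and 96.8% by normal approximation). The point does not depend on them; they supply the scale.

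**4. Size if later data enter (assumed inputs).** Let s be the shift in a starter's score, and let every starter have a Week 52 score carrying the full shift. Change in the apparent HMTM benefit = s × (HMTM start rate − control start rate).
- HMTM 5%, control 10%: s = 1 gives −0.05; s = 3 gives −0.15.
- HMTM 10%, control 5%: +0.05 to +0.15.
- Equal rates: 0.

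Against the 2.6-unit ADAS-cog11 target, 0.05 to 0.15 is about 2% to 6%.

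**5. Size if starters are left out of the weights (assumed inputs).** Let a fraction f of the HMTM arm start, with last on-treatment visit at week w and the effect accruing linearly. Counting them gives I = E52·(1 − f) + E52·(w/52)·f; leaving them out gives E52. Power is for n = 150 per arm, normal approximation, standard error unchanged.

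| f, last visit | ADCS-ADL23 I (E52 = 3.4) | ADAS-cog11 I (E52 = 2.6) | Overstatement | Power, ADCS-ADL23 |
|---|---|---|---|---|
| 2%, Week 39 | 3.383 | 2.587 | 0.5% | 93.1% |
| 5%, Week 26 | 3.315 | 2.535 | 2.6% | 92.2% |
| 10%, Week 26 | 3.230 | 2.470 | 5.3% | 90.8% |
| 10%, Baseline | 3.060 | 2.340 | 11.1% | 87.7% |

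Steps 4 and 5 are separate illustrations. The two effects can run in opposite directions and need not cancel.

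**The case against.** - **The SAP does not say that on-drug scores enter the ITTv5 model.** It states the no-start assumption expressly, the use of later data arrives only by cross-reference to a rule written for study withdrawals, and 5.9.2.2 takes its model from the MITT section. This stands to a degree: the text permits such scores rather than requiring them. But nothing for ITTv5 excludes them, and the protocol did.
- **Starters may already be in the weights.** The count turns on having no later on-treatment assessment, and Section 5 defines on-treatment as off AChEI/memantine. A reader might infer from 5.9.2.2 that starters are deliberately left out. The documents do not support that as settled, because 5.9.1.1 says the opposite and the protocol's weights are worded the same way. It is a contradiction to resolve.
- **Direction.** A reader might infer that the treatment difference is pulled toward zero. That requires more starts on control than on HMTM, which no document states; omission from the weights would inflate the effect.
- **Exposure is limited.** MITTv5 comes first in the sequence and excludes these scores, and the while-on-treatment estimand uses the last on-treatment value. Both are true, and neither protects the EMA-primary estimate.
- **PET differs.** Its ICE #2 rule carries no clause using later data, and it has a single withdrawal count. So PET is silent on later data rather than permissive, and needs its own wording.

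**Conclusion.** Wrong as written on later data: the SAP omits an exclusion that the protocol states in 17.4.4 and supports in 17.4.3 and 17.4.11.3. The EMA-primary estimand can therefore draw on scores that its own assumption rules out. On the weights, SAP 5.9.1.1 and 5.9.2.2 contradict each other.

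The bias can be neither signed nor sized from the documents. The ranges of 0.05 to 0.15 units and 0.5% to 11.1% rest wholly on assumed start rates, an assumed 1 to 3 unit shift and linear accrual. The 5% in SAP 5.9.2.1 is only a trigger for a supplementary analysis, not an expected rate.

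A reader might also infer that the clause was removed after unblinding, since SAP v3.0 postdates it. Neither the modification history nor Section 10 says when the wording changed, so that inference is not supported.

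**What to change.** 1. In SAP 5.9.1.1, Events 3, restore the protocol's exclusion of data after the event. The MRI estimand inherits it by reference. Add the same clause to Events 3 of the PET estimand (5.9.1.5).
2. In SAP 5.9.2.2, state that the primary-analysis counts nw0 to nw39 include Events 3 subjects by their last on-treatment visit as defined in Section 5, with that definition's short-term-use exception.
3. For PET (5.9.3.2), include these subjects in the single count nw.
4. List the correction in SAP Section 10 as an alignment with Protocol 17.4.4. Because SAP v3.0 postdates partial unblinding, report the estimate under both readings so that the effect of the choice is visible.

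The cost is a few lines of text, a changed count in the contrast, a few observations lost and one extra run.

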#### 5.9.1.2. Primary Estimand (ITT)

The Primary Estimand (ITT) is designed to answer the question on the treatment effect of HMTM dose of 16 mg/day as monotherapy versus control (with and/or without MTC) in the targeted population of subjects with probable AD and MCI-AD at Week 52, regardless of trial product discontinuation and enrollment before or after protocol version 5.0.

This estimand is constructed in line with ICH E9 (R1) addendum. The five components defining the estimand of interest are:

- A. Treatment:** Up to 52 weeks HMTM dose of 16 mg/day as monotherapy or matching control (with and/or without MTC).
- B. Population:** Subjects with probable AD and MCI-AD as described by the inclusion and exclusion criteria.
- C. Patient-level outcomes / variables:** The co-primary outcomes are the change from Baseline of the ADAS-cog11 and ADCS-ADL23 at Week 52.
- D. Population-level summary:** Population weighted least squares means difference.

Sponsor:	TauRx Therapeutics Ltd.		
Protocol:	TRx-237-039		
Document Version No.:	3.0	Document Date:	07-JUN-2023

**E. Intercurrent Events:** Identification and handling of ICE as described for the primary estimand (see Section 5.9.1.1), excluding the sensitivity analyses.

